### Data collection and management

Data will be collected through questionnaires at baseline and every six months up to three months after the adolescent's transfer to adult care (Figure 2). Transfer time is registered as the date for the last consultation at paediatric. Questionnaires will be sent out via email or by post based on participants' wishes. The questionnaires will take approximate 10 minutes to complete. All data will be handled confidential and stored in the password protected software REDCap.

**Figure 2** Model of time frame

Questionnaires	Time frame				
	Baseline	6 months	12 months	Transfer	3 months follow-up
Socio-demographic					
Parents	X				
Transition readiness (TR)					
Parents	X	X	X	X	X
Adolescent	X	X	X	X	X
Allocation of Responsibility (AoR)					
Parents	X	X	X	X	X
Adolescent	X	X	X	X	X
The Uncertainty Scale					
Parents	X			X	
EQ-5D-5L					
Adolescent	X			X	X
Experiences of transfer					
Parents					X
Transfer satisfaction					
Parents					X
Adolescent					X

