### **Missing data, drop out and lost to follow up**

Loss to follow-up and missing data for various reasons is impossible to avoid in randomized trials. We will apply the analysis framework in which missing data related to the intention-to-treat approach depend on making plausible assumptions about the missingness of the data and including all participants in subsequent sensitivity analyses.

1. Attempt to follow up all randomized parents, even if they withdraw from allocated treatment.
2. Perform a main analysis of all observed data that are valid under a plausible assumption about the missingness of the data (i.e., Model-based: data as observed; using linear mixed effects models, assuming that data are 'Missing at Random' [MAR]).
3. Perform sensitivity analyses to explore the effect of departures from the assumption made in the main (#2) analysis (i.e., a non-responder-imputation: using the value at baseline to replace missing data will correspond to a non-responder imputation; these models will potentially be informative even if data are 'Missing Not At Random' [MNAR]).
4. Account for all randomized parents, at least in the sensitivity analyses (covered by #2 and #3 above, plus the corresponding analyses based on the per protocol population).

The interpretation of the corresponding statistical measures of uncertainty of the treatment effect and treatment comparisons will involve consideration of the potential contribution of bias to the P-value, 95% confidence interval, and of the inference in general.

Our primary analysis population will be all parents with available data at baseline, statistically modelled using repeated-measures linear mixed effects models (see above). These models will be valid if data are 'MAR'.

*Sensitivity:* We will analyze all variables, with missing data being handled by multiple imputation techniques.

When the different sensitivity analyses agree, and the analyses on the sensitivity analyses and the main analysis lead to essentially the same conclusions, confidence in the trial results is increased.

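### The main analysis promises all observed data but is then limited to parents with a baseline score, and the analyses item 4 cites cannot reach the parents this drops

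*Protocol*

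**What the plan says.** All the wording at issue is in the protocol section on missing data, drop-out and loss to follow-up.

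- **Item 2:** "Perform a main analysis of all observed data", by linear mixed model under MAR.
- **Item 3:** a sensitivity analysis for departures from MAR. The one method named, introduced by *i.e.*, is a baseline fill: "using the value at baseline to replace missing data will correspond to a non-responder imputation". The protocol says only that it may be informative if data are missing not at random.
- **Item 4:** "Account for all randomized parents, at least in the sensitivity analyses (covered by #2 and #3 above", and then "plus the corresponding analyses based on the per protocol population").
- **Population sentence, after the list:** "Our primary analysis population will be all parents with available data at baseline", analysed with repeated-measures mixed models.
- **Sensitivity sentence, directly after that:** "We will analyze all variables, with missing data being handled by multiple imputation techniques".
- **Closing sentence:** if the analyses "lead to essentially the same conclusions, confidence in the trial results is increased".

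On timing, the section on data collection says: "Data will be collected through questionnaires at baseline and every six months up to three months after" transfer. Its time-frame table schedules parent transition readiness (TR) at baseline, 6 months, 12 months, transfer and three months after transfer. Questionnaires go out by email or post. The randomisation section places randomisation after screening and consent. Its text does not make a completed baseline questionnaire a condition.

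**The concern.** Item 2 and the population sentence define different sets. A parent with any of the four later TR scores but no baseline belongs to the first set and not to the second. The plan thus selects randomised parents by data availability in its main analysis, although the chosen type of model does not require it.

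Item 4 then gives an assurance that its own references do not deliver. A reader would take it that every randomised parent is covered somewhere among items 2 and 3 and the per-protocol analyses. For parents without a baseline that is not so.

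At stake are some precision, possible bias if baseline non-response differs between arms, and a statement about coverage that the trial report could not truthfully repeat. A lesser matter is that item 3 ties the whole question of departures from MAR to one fixed fill, while the closing sentence draws confidence from agreement between analyses.

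**Working it through.** **1. The plan's own figure.** The sample size section uses a difference of 0.50, SD 0.68, power 0.80 and alpha 0.05. A two-sided two-sample t-test needs 30.03 per group, rounded up to 31, or 62 in total. This reproduces, with power 0.813 at 31 per group. No stated figure is wrong.

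**2. Which analyses reach a parent with follow-up but no baseline?**

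| Analysis | Reaches this parent? |
|---|---|
| Item 2, with the population sentence applied | No, excluded by definition |
| Item 3, baseline fill | No, there is no baseline value to carry forward |
| Per-protocol set | No, a restriction cannot add anyone |
| Multiple imputation | It could, but item 4 does not cite it |

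**3. Cost in precision under a mixed model.** Assumptions: five TR occasions, equal correlation r between any two, a common baseline mean across arms, 31 per arm, and a fraction f = 0.10 without a baseline. The protocol gives neither r nor f.

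- Dropped: SE = 0.68 × √[2(1 − r²)/27.9], where 27.9 = 31 × 0.9.
- Kept: SE² = (2 × 0.68²/31) × [1 − r²/(R² + (1 − R²)/(1 − f))], where R² = 4r²/(1 + 3r) is the share of baseline variance explained by the four later scores.

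At r = 0.5, R² = 1/2.5 = 0.40. The denominator is 0.40 + 0.60/0.90 = 1.067, and the bracket is 1 − 0.25/1.067 = 0.766. With 2 × 0.68²/31 = 0.02983, SE = √(0.02983 × 0.766) = 0.151. Dropped, SE = 0.158. With no missing baselines it is 0.150.

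Power for a difference of 0.50 (two-sided t, degrees of freedom = parents analysed minus 3):

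| r | SE kept | SE dropped | Power kept | Power dropped | Loss |
|---|---|---|---|---|---|
| 0.3 | 0.165 | 0.174 | 0.844 | 0.807 | 0.037 |
| 0.5 | 0.151 | 0.158 | 0.902 | 0.876 | 0.026 |
| 0.7 | 0.126 | 0.130 | 0.975 | 0.965 | 0.010 |

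Parents recruited close to transfer will have fewer than five occasions. With a single follow-up at r = 0.5, R² = 0.25 and the kept SE is 0.1515 instead of 0.1511, so the picture does not change.

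**4. Possible bias.** If a fraction p of one arm only is dropped and those parents score 0.5 below the rest of their arm, the estimate moves by 0.5p. That is 0.025 at p = 5% and 0.05 at p = 10%. If the missingness is alike in both arms, the two shifts cancel.

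**5. The baseline fill (secondary).** Let m be the mean rise in controls, d the true difference, and L_I and L_C the loss in the intervention and control arms. Under loss unrelated to outcome, the fill estimates (1 − L_I)(m + d) − (1 − L_C)m.

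- d = 0, m = 0.4, loss 10%/30%: 0.9 × 0.4 − 0.7 × 0.4 = +0.08. With 30%/10% it is −0.08.
- d = 0.5, m = 0, loss 20%/20%: 0.8 × 0.5 = 0.40.
- d = 0 with equal loss: no shift.

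In simulation of the ±0.08 case (31 per arm, SD 0.68, follow-up regressed on arm and baseline, r from 0.3 to 0.7), the fill rejected a true null in about 8% to 11% of trials (about 9% at r = 0.5). Analysis of the observed scores stayed unbiased at about 5%. The loss rates and the rise are assumptions.

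**The case against.** Several stronger readings are tempting, and the documents do not support them.

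- **That the exclusion breaks the plan's intention-to-treat approach.** The protocol's own framework requires all participants only in the sensitivity analyses, and item 4 repeats this. The conflict is with item 2's wording and item 4's references.
- **That no analysis reaches these parents.** The multiple imputation sentence follows directly on the population sentence and may well cover them. What fails is item 4's list.
- **That missing baselines will occur.** Nothing shows this. The abstract calls baseline pre-intervention, and the figure in the randomisation section could not be read here and might place baseline before allocation. If so, exclusion rests on a pre-randomisation variable and costs precision, not validity.
- **That power falls below 0.80.** An unadjusted t-test would drop from 0.81 to 0.77 at 10% missing, but that is not the planned model. Under the mixed model, power stays above 0.80 at every correlation tried.
- **That the baseline fill is an error, or that main analysis and fill will agree while both are wrong.** The protocol claims only that the fill may be informative. Agreement on a false result can be constructed. With a true effect of 0, 20% loss per arm, lost intervention parents 0.5 below and lost controls 0.5 above their MAR value, the main analysis gives 0.20 and the fill 0.16, both significant in about 18% of trials. But that is a chosen divergence of 1.0 point (1.0/0.68 = 1.5 SD). If only the intervention arm is shifted, with d = 0.5 among responders and m = 0, the truth is 0.5 − 0.2 × 0.5 = 0.40, exactly what the fill gives.

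It is also fair that shift grids and tipping points are commonly left to the SAP. What remains is the contradiction on the population and item 4's failed references, both already fixed in the protocol's words.

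**Conclusion.** The point holds as a correctable inconsistency of modest size. The primary population is narrower than item 2 promises, and the analyses item 4 cites cannot account for a randomised parent without a baseline. At an assumed 10% missing baselines and correlations of 0.3 to 0.7, the power loss is about 0.01 to 0.04. Bias arises only if the missingness differs by arm, for which the documents give no evidence. If nearly all baselines are completed, the practical effect is negligible. The change is still worth making because it uses data already scheduled.

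The reliance on a single baseline fill is a secondary weakness and not an error. Under MAR and no true effect it can move the estimate by about ±0.08 in the assumed case, so agreement or disagreement with it is a weak guide to robustness.

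**What to change.** 1. Define the primary population as all randomised parents.
2. Put baseline TR in the outcome vector of the mixed model with a common mean across arms, so that any parent with at least one score contributes.
3. In item 4, cite multiple imputation as the analysis that covers missing baselines and parents with no scores.
4. Secondary: label the baseline fill a no-change scenario and add delta-adjusted multiple imputation by arm as the analysis for departures from MAR. The grid of shifts can be left to the SAP.

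The protocol schedules the SAP for after all participants have completed the final measurement. Correcting the wording now keeps these choices clearly prespecified. The cost is a few sentences and a little more programming, with no new data and no change to recruitment.

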## Discussion

In the last decade, there has been an increased focus on transition programmes targeting chronically ill adolescents (Gabriel, McManus et al. 2017, Burke, Kirkham et al. 2018, Schmidt, Ilango et al. 2020). Although parents play a significant role regarding medication and treatment in the case of paediatric chronic illness, there is still a lack of structured programmes to support parents during their child's transition, including transfer from paediatric to adult care. To our knowledge, this is the first intervention that target parents of chronically ill adolescents during their child's transition to adult care tested in a randomised trial. Our intervention is developed based on the hypothesis, that a nurse-led transfer intervention targeting parents will both improve the parents' readiness for their child's transition to adult health care and strengthen the adolescent's self-management skills. Our setup with both measurements from the parents and the adolescents will give us the opportunity to examine if ParTNer-STEPs is effective in increasing parents' and adolescents' transition readiness, reducing parental uncertainty and facilitating a shift of treatment responsibility from the parents to the chronically ill adolescent.

The intervention will be evaluated in multiple outpatient clinics across paediatric and adult care and performed by clinic staff with an interdisciplinary background in a real-life clinical setting. On that background, we have chosen a complex intervention design as the intervention will involve several interacting components (Craig, Dieppe et al. 2013, Craig, Dieppe et al. 2019). During the development phase we used participatory design to involve relevant stakeholders (parents, adolescents, and HCP) in the development of the program due to the absence of transfer interventions targeting parents. (Simonsen and Robertson 2013, Clemensen, Rothmann et al. 2017). Thus, we ensured the users' (parents) needs were being represented and met in the program by incorporating the principles of participatory design in the development of the intervention. Furthermore, the involvement of HCP secured the feasibility and relevance of the interventions in the clinical practice and increased the chances of successful implementation (Garne Holm, Brødsgaard et al. 2017).

Despite these efforts, the complexity of our intervention including multiple components, many stakeholders and different settings) may affect our results considerable. This is an area we will address during our discussion of the major findings. We will also, in line with the MRC recommendation, conduct a process evaluation, which will be reported subsequently.

A part of the intervention (the transfer consultations) will take place in the clinic and out of our control, why the performance/ execution of this part relay on the HCP participation and willingness to adhere to the consultation scripts. Thus, daily clinical issues as staff shortage, problems in the interprofessional cooperation and time pressure might hinder the HCP in conducting the intervention as described. We have tried to prevent this by including the HCP in the development of the intervention with continuous discussions of realistic workflows and resources. We will also be in close contact with the HCP during the intervention in order to detect and act on possible barriers/challenges e.g. vacancies.

## Trial status

Recruitment starts in July 2021 and is ongoing.

## Abbreviations

HCP: Health Care Professionals; RCT; Randomized Control Trail; TR: Transition Readiness; AoR: Allocation of Responsibility; SAP: Statistical Analysis Plan; MAR: Missing At Random; MNAR: Missing Not At Random'.

## Declarations

### Ethics approval and consent to participate

The project will adhere to the regulations established by the Ethical Guidelines for Nursing Research in the Nordic Countries, all relevant laws and regulations in Denmark, and to the Declaration of Helsinki II (World-Medical-Association, 2008) and is approved by the Danish Data Protection Agency, reference no. VD-2018-396. We have formally enquired the regional research ethics committee with a full clinical description of the project. They have reviewed the project and given us permission to perform the study (reference no. FSP 20031083). According to Danish legislation studies such as register research projects, interview surveys and questionnaire surveys can be performed without formal ethical approval cf. section 1 and 2 in the committee law as no human biological material is included (National Committee for Health Research Ethics <https://en.nvk.dk/rules-and-guidelines/act-on-research-ethics-review-of-health-research-projects>).

Before obtaining consent from the parents, ELT will provide all participants with oral and written information of the study, including the fact that they can withdraw from the study at any time without consequences for their child's treatment. We will carefully consider the risk of coercion, autonomy, and confidentiality. Written, informed consent to participate will be obtained from all participants.

### Consent for publication

Not applicable.

### Availability of data and materials

Data will be made available from corresponding author on reasonable request.

### Competing interests

The authors declare that they have no competing interests.

### Funding

This project is funded by the Novo Nordisk Foundation in the call "PhD Scholarships in Nursing Research 2019" (grant reference number is NNF19OC0058145) and Dagmar Marshalls Fond. Both fond has not had any role in the design of the study as outlines in this protocol and will not have a role in data collection, analysis of data, interpretation of data and dissemination of findings.

